7.2 Disposition of Participants

The number and percentage of participants in each category (screened, randomized, study complete and study discontinuation, the reasons of screened failure and discontinuation, participants in each analysis set) will be summarized. Screened failure participants, discontinued participants and participants excluded from each analysis set will be listed, respectively.

7.3 Compliance

Descriptive statistics of whether completed each vaccination, whether completed the immunogenicity blood collection will be presented for each group.

Protocol deviations/violations by total and classification will be summarized by number of events, number of participants, and percentage of participants for each group. Fisher's exact test will be used to test the differences among groups. All protocol deviations/violations will be listed.

The above analysis will be analyzed based on all randomised participants.

7.4 Demographics and baseline Characteristics

Descriptive statistics will be used to summarize demographics and baseline variables as follows:

- **Demographics:** gender, race, ethnic and age.
- **Vital signs:** height, weight, axillary temperature, heart rate and breathing rate.
- **Clinical characteristics:** medical history, Severe Acute Respiratory Syndrome-Coronavirus (SARS-CoV-2) rapid antigen test, prior medications/ vaccines.

Analysis of Variance (ANOVA) will be used to compare continuous variables (including age, height, weight, axillary temperature, heart rate and breathing rate) among groups. Chi-square test/ Fisher's exact test will be used to compare categorical variables (including gender, race, ethnic, whether has

medical history and results of SARS-CoV-2 test) among groups.

Medical histories will be summarized by number of events, number of participants, and percentage of participants, and tabulated by System of Class (SOC) and Preferred Term (PT). Fisher's exact test will be used to test the differences among groups.

Demographics, vital signs, medical history and results of SARS-CoV-2 rapid antigen tests will be listed, respectively.

The above analysis will be analyzed based on FAS and PPS.

7.5 Prior and Concomitant Medications/ Vaccines

Prior and concomitant medications will be summarized by number of events, number of participants, and percentage of participants, and tabulated by Anatomic Therapeutic Chemical classification (ATC2) and Preferred Name (PN). Fisher's exact test will be used to test the differences among groups.

Prior and concomitant vaccines will be summarized by number of events, number of participants, and percentage of participants, and tabulated by ATC4 and PN. Fisher's exact test will be used to test the differences among groups.

The prior and concomitant medications/ vaccines will be listed.

The prior medications and vaccines will be analyzed based on FAS and PPS. The concomitant medications and vaccines will be analyzed based on SS.

7.6 Study Hypothesis

The following research hypothesis will be considered for the immunogenicity evaluation of **group C1** and **group S1**:

➤ **Hypothesis test I:** At 28 days after full vaccination, group C1 will have a non-inferior seroconversion (4-fold increase) rate of Nab against polioviruses to group S1, ie:

$$\text{Null hypothesis } H_0: \pi_{C1j,d28} - \pi_{S1j,d28} \leq \Delta_1$$

$$\text{Alternative hypothesis } H_1: \pi_{C1j,d28} - \pi_{S1j,d28} > \Delta_1$$

Where $j = 3$ serotypes of Nab against polioviruses (including type 1, 2 and 3). $\pi_{C1j,d28}$, and $\pi_{S1j,d28}$ represent the seroconversion (4-fold increase) rate of type- j Nab against polioviruses at 28 days after full vaccination in group C1 and group S1, respectively, with the non-inferiority criterion Δ_1 is -10%, and a one-sided α is 0.025.

7.7 Immunogenicity Evaluation

➤ **Immunogenicity evaluation for Nab against polioviruses**

The following analysis will be performed for Nab against polioviruses of serotype I, II, III between **group C1 and group S1 at 28 days after last vaccination of sIPV**, respectively:

The seroconversion (4-fold increase) rate in all participants, SCR in seronegative participants at pre-vaccination, 4-fold increase rate in seropositive participants at pre-vaccination and SPR in all participants will be estimated in each group. Clopper Pearson method will be used to calculate 95% CIs and Cochran-Mantel-Haenszel- χ^2 (CMH- χ^2) test stratified by study site (including Bangladesh 01, Pakistan 01 and Pakistan 02) will be used to test the differences between the two groups. The CMH method will be used to calculate the rate difference between (group C1 - group S1) and 95% CIs. Non-inferiority will be concluded if the lower limit of the 95% CI of SCR difference between group C1 and Group S1 >-10%.

Analysis of covariance model will be modeled to analyze Nab level against polioviruses at 28 days after last vaccination of sIPV. In this model, the log-transformed Nab data against polioviruses at 28 days after last vaccination of sIPV will be included as dependent variable, the log-transformed Nab data before vaccination as a covariate, and treatment group (including C1 and S1) and study site (including Bangladesh 01, Pakistan 01 and Pakistan 02) are the fixed effect. From the model, the LS-adjusted log-transformed Nab level against polioviruses at 28 days after last vaccination of sIPV in each group and the difference between (group C1 - group S1) will be calculated. The adjusted GMT at 28 days after last vaccination of sIPV in each group, GMT ratio between (group C1/group S1), and its 95% CIs will be obtained after inverse log-transformation.

Descriptive statistics, including geometric mean and 95% CIs, for GMT and GMFR in all participants, seronegative participants at pre-vaccination and seropositive participants at pre-vaccination will be presented by groups. The group t-test after log-transformation will be used to compare the differences between groups. The ratio of GMT between groups and their 95% CIs will be estimated as well.

The forest plot of the post-vaccination seroconversion (4-fold increase) rate for all participants in comparison (group C1 and group S1) will be plotted.

The reverse cumulative distribution plot of antibody titers at pre- and post-vaccination time points will be plotted.

The above analysis will be based on the FAS and PPS.

➤ **Immunogenicity evaluation for IgG antibodies against pertussis**

The following analysis will be performed for IgG antibodies against PT, FHA and PRN of **group C2 and group S2 at 28 days after last vaccination of DTP-HepB-Hib**, respectively:

The seropositivity rate and SCR for all participants will be estimated by groups. The Clopper Pearson method will be used to calculate 95% CIs and the CMH- χ^2 test considering the study site (including Bangladesh 01, Pakistan 01 and Pakistan 02) as a stratification factor will be used to test the differences between groups. The CMH- χ^2 method will be used to calculate the rate difference between (group C2 - group S2) and 95% CIs.

Analysis of covariance model will be modeled to analyze IgG antibody level against PT, FHA and PRN at 28 days after last vaccination of DTP-HepB-Hib. In this model, the log-transformed IgG antibody data against PT, FHA and PRN at 28 days after last vaccination of DTP-HepB-Hib will be included as dependent variable, the log-transformed IgG antibody data before vaccination as a covariate, and treatment group (including C2 and S2) and study site (including Bangladesh and Pakistan) are the fixed effect. From the model, the LS-adjusted log-transformed IgG antibody level against PT, FHA and PRN at 28 days after last vaccination of DTP-HepB-Hib in each group and the difference between (group C2 - group S2) will be calculated. The adjusted GMC at 28 days after last vaccination of DTP-HepB-Hib in each group, GMC ratio between (group C2/group S2), and its 95% CIs will be obtained after inverse log-transformation.

Descriptive statistics, including geometric mean and 95% CIs, for GMC and GMFR of all participants will be presented by groups. The grouped t-test after log-transformation will be used to compare the differences between groups. The ratio of GMC between groups and their 95% CIs will be estimated as well.

The reverse cumulative distribution plot of antibody concentrations at pre- and post-vaccination time points will be plotted.

The above analysis will be based on the FAS and PPS.

➤ **Immunogenicity evaluation for IgG antibodies against diphtheria, tetanus, HepB, Hib and pneumococcal**

The following analysis will be performed for IgG antibodies against diphtheria, tetanus, HepB, Hib and pneumococcal (including serotypes of 1, 5, 6B, 14 and 19F) of **group C2 and group S2 at 28 days after last vaccination of DTP-HepB-Hib and PCV**, respectively:

The SPR for all participants will be estimated by groups. The Clopper Pearson method will be used to calculate 95% CIs and the CMH- χ^2 test considering the study site (including Bangladesh 01, Pakistan 01 and Pakistan 02) as a stratification factor will be used to test the differences between groups.

Analysis of covariance model will be modeled to analyze IgG antibodies against diphtheria, tetanus, HepB, Hib and pneumococcal (including serotypes of 1, 5, 6B, 14 and 19F) at 28 days after last vaccination of DTP-HepB-Hib. In this model, the log-transformed IgG antibodies against diphtheria, tetanus, HepB, Hib and pneumococcal (including serotypes of 1, 5, 6B, 14 and 19F) at 28 days after last vaccination of DTP-HepB-Hib will be included as dependent variable, the log-transformed IgG antibody data before vaccination as a covariate, and treatment group (including C2 and S2) and study site (including Bangladesh and Pakistan) are the fixed effect. From the model, the LS-adjusted log-transformed IgG antibodies against diphtheria, tetanus, HepB, Hib and pneumococcal (including serotypes of 1, 5, 6B, 14 and 19F) at 28 days after last vaccination of DTP-HepB-Hib in each group and the difference between (group C2 - group S2) will be calculated. The adjusted GMC at 28 days after last vaccination of DTP-HepB-Hib in each group, GMC ratio between (group C2/group S2), and its 95% CIs will be obtained after inverse log-transformation.

Descriptive statistics, including geometric mean and 95% CIs, for GMC and GMFR of all participants will be presented by groups. The grouped t-test after log-transformation will be used to compare the differences between groups. The ratio of GMC between groups and their 95% CIs will be estimated as well.

The reverse cumulative distribution plot of antibody concentrations at pre- and post-vaccination time points will be plotted.

The above analysis will be based on the FAS and PPS.

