9.3.4 Immunogenicity Analysis

Analysis for immunogenicity against Polio

Seroconversion rate and sero-protection rate on day 28 after the last vaccination of sIPV will be estimated, and the corresponding 95% CIs will be derived from Clopper Pearson method.

The difference of seroconversion rates between co-administration group and staggered administration group will be compared using Cochran-Mantel-Haenszel- χ^2 (CMH- χ^2) test stratified by study site. The CMH- χ^2 method will be used to calculate the rate difference between (group C1 and group S1) and 95% CIs. Non-inferiority will be concluded if the lower limit of the 95% CI of rate difference (co-administration group-staggered administration group) $>-10\%$.

The descriptive statistics, including GMT and GMFR and corresponding 95% CIs are employed to summarize the immunogenicity data. The t-tests after log transformation will be used to compare two groups. The GMT ratio between two groups and the corresponding 95% CIs will be estimated as well.

Analysis for immunogenicity against Diphtheria, Tetanus, Pertussis

Seropositivity/sero-protection rate against Diphtheria, Tetanus and Pertussis on day 28 after the last vaccination of DTP-HepB-Hib vaccine will be estimated and the corresponding 95% CIs will be derived from Clopper Pearson method. The difference of seropositivity/sero-protection rate between co-administration group and staggered administration group will be Cochran-Mantel-Haenszel- χ^2 (CMH- χ^2) test stratified by study site. The CMH- χ^2 method will be used to calculate the rate difference between (group C2 and group S2) and 95% CIs. Non-inferiority will be concluded if the lower limit of the 95% CI of rate difference (co-administration group-staggered administration group) $>-10\%$.

The descriptive statistics, including GMC and GMFR and corresponding 95% CIs are employed to summarize the immunogenicity data. The t-tests after log transformation will be used to compare two groups. The GMC ratio of two groups and the corresponding 95% CIs will be estimated as well.

Analysis for immunogenicity against HepB, Hib, Pneumococcal

Sero-protection rates at day 28 after the last vaccination will be estimated and the corresponding 95% CIs will be derived from Clopper Pearson method. The Chi-square tests/Fisher Exact test will be used

to compare the sero-protection rates between two groups.

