4.1.2 Immunogenicity Observation

About 3 ml venous blood will be collected before the first vaccination and 28 days (+7 days) after the last vaccination of sIPV or routine vaccines. Group C1 and S1 will be compared in terms of immunogenicity against polio, Group C2 and S2 will be compared in terms of immunogenicity against diphtheria, Tetanus, Pertussis, Hepatitis B, Hib and Pneumococcal.

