5.1 Immunogenicity Endpoints

➤ **In the comparison between group C1 and group S1**, the immunogenicity endpoints for neutralizing antibody (Nab) against polioviruses of serotype I, II, III at 28 days after last vaccination of sIPV will be defined as follows, respectively:

- (1) **Seroconversion (4-fold increase) rate**, which is defined as pre-vaccination Nab titer against polioviruses $<1:8$ and post-vaccination Nab titer against polioviruses $\geq 1:8$, or 4-fold Nab titer against polioviruses increase in case that pre-vaccination Nab titer against polioviruses $\geq 1:8$.
- (2) **Seroconversion Rate (SCR) in seronegative participants at pre-vaccination**, which is defined as pre-vaccination Nab titer against polioviruses $<1:8$ and post-vaccination Nab titer against polioviruses $\geq 1:8$.
- (3) **4-fold increase rate in seropositive participants at pre-vaccination**, which is defined as 4-fold Nab titer against polioviruses increase in case that pre-vaccination Nab titer against polioviruses $\geq 1:8$.
- (4) **Sero-Protection Rate (SPR)**, which is defined as Nab titer against polioviruses $\geq 1:8$.

(5) **Geometric Mean Titer (GMT) and Geometric Mean Fold Rise (GMFR)**, which is defined as the increase of Nab titers against polioviruses after vaccination compared to baseline.

(6) **GMT and GMFR in seronegative participants at pre-vaccination**

(7) **GMT and GMFR in seropositive participants at pre-vaccination**

➤ **In the comparison between group C2 and group S2**, the immunogenicity endpoints for Immunoglobulin G (IgG) antibody against Pertussis Toxin (PT), Filamentous Hemagglutinin (FHA) and Pertactin (PRN) at 28 days after last vaccination of DTP-HepB-Hib will be defined as follows, respectively:

- (1) **Seropositivity rate**, which is defined as IgG antibody concentration after vaccination ≥ 20 EU/ml.
- (2) **SCR**, which is defined as pre-vaccination IgG antibody concentration < 5 EU/ml and post-vaccination concentration ≥ 20 EU/ml, or 5 EU/ml \leq pre-vaccination IgG antibody concentration

<20 EU/ml and 4-fold concentration increase, or pre-vaccination IgG antibody concentration \geq 20 EU/ml and 2-fold concentration increase.

(3) Geometric Mean Concentration (GMC) and GMFR, which is defined as the increase of IgG antibody concentrations after vaccination compare to baseline.

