5.2 Safety Endpoints

(1) Adverse Events

➤ **Solicited Adverse Events:** including solicited local (vaccination site) and systemic AEs that occur during 7 days after each vaccination. The solicited local (vaccination site) AEs: including redness, swelling, rashes, induration and pruritus. The solicited systemic AEs: including fever, acute allergic reaction, diarrhea, decreased appetite, irritability, and decreased activity.

➤ **Unsolicited Adverse Events:** including all AEs except solicited AEs during the solicitation period, and all AEs during the non-solicitation period.

(2) Serious Adverse Events

6 Analysis Sets

(1) Full Analysis Set (FAS): Following the principle of Intention to Treat (ITT), it includes all participants who are randomized, complete at least one vaccination against the antigen to be evaluated, and have the valid immunogenicity results before the first vaccination. The participants who are vaccinated erroneously will be analyzed for the immunogenicity evaluation as randomized according to the ITT principle.

(2) Per Protocol Set (PPS): It is a subset of FAS which including all the participants who are eligible for this study according to the inclusion and exclusion criteria, and then randomized, complete full vaccination as protocol specified, and have valid immunogenicity results before and after the vaccination. Participants who meet the following conditions will be excluded from PPS:

- Those who has significant protocol deviations;
- Those who are vaccinated with the wrong vaccine;
- Use of protocol prohibited vaccines or drugs;
 - Other investigational or unlicensed products (drugs or vaccines);
 - Long-term use (lasting more than 14 days) of immunosuppressive or other immunomodulatory drugs (inhaled or topical steroids are allowed);
 - Immunoglobulin and/or blood preparations;
- Newly diagnosed autoimmune disease, including human immunodeficiency virus (HIV) infection;
- Other situations affecting the evaluation of vaccine immunogenicity.

For group C1 and S1, FAS and PPS will be defined for Nab against polioviruses of serotype I, II, III, respectively. For group C2 and S2, FAS and PPS will be defined for IgG antibodies of diphtheria, tetanus, pertussis (including PT, FHA and PRN), hepatitis B, Hib and pneumococcal (including serotypes of 1, 5, 6B, 14 and 19F), respectively.

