7.9 Handling of Missing Data

- The missing values of immunogenicity analysis in FAS will be imputed by using Last Observation Carried Forward (LOCF) method.
- The missing values of safety evaluation will not be imputed in this study.

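### SAP 7.6 and 7.7 do not carry out the protocol's non-inferiority rule for diphtheria, tetanus and pertussis; site coding and polio precision can also be improved cheaply

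*SAP*

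**What the plan says.** **Diphtheria, tetanus, pertussis.** Protocol section 3 and SAP 3.2 list non-inferiority for these antigens as secondary objectives. Protocol 9.3.4 decides it by the C2-S2 rate difference, stratified by site, with the lower 95% limit above -10%. SAP 7.7 treats pertussis in one block and diphtheria and tetanus in another, together with hepatitis B, Hib and pneumococcal. SAP 7.6 contains one hypothesis, for polio. SAP 2.3 says the planned analyses agree with the protocol.

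**Site.** SAP 4.2 stratifies randomisation by study site. The CMH tests and the polio ANCOVA in SAP 7.7 name three sites (Bangladesh 01, Pakistan 01, Pakistan 02). The two C2/S2 ANCOVAs list Bangladesh and Pakistan as the levels of study site.

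**Primary polio difference.** SAP 7.7: "The CMH method will be used to calculate the rate difference between (group C1 - group S1) and 95% CIs". Protocol 9.3.4 is similar: a CMH chi-square "method will be used to calculate the rate difference between (group C1 and group S1) and 95% CIs". Both stratify by site only, and neither names a variance or interval formula. SAP 5.1 defines seroconversion as reaching 1:8 from a baseline below 1:8, "or 4-fold Nab titer against polioviruses increase in case that pre-vaccination Nab titer against polioviruses" is at least 1:8. The FAS requires that infants "have the valid immunogenicity results before the first vaccination" (SAP section 6). SAP 7.7 already reports "SCR in seronegative participants at pre-vaccination, 4-fold increase rate in seropositive participants at pre-vaccination" and adjusts GMT for baseline titre. Blood is "collected before the first vaccination and 28 days (+7 days) after the last vaccination of sIPV or routine vaccines" (SAP 4.1.2). On missing data, SAP 7.9 says: "The missing values of immunogenicity analysis in FAS will be imputed by using Last Observation Carried Forward (LOCF) method". On analysis sets, SAP 7.7 says: "The above analysis will be based on the FAS and PPS".

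**The concern.** A CMH test asks whether two rates differ; it cannot show that one is no more than 10 points below the other. If the tables follow the SAP as written, the diphtheria and tetanus objectives would have no statistic that answers them, and pertussis would have an interval with no stated criterion. The missing pieces would then be added after the data are seen, or left out.

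The other two items concern efficiency and tidiness. A country term drops the distinction between the two Pakistan sites, which randomisation respected. Baseline serostatus is collected before the first dose, determines which rule the infant must meet, and is probably related to the outcome, so leaving it out of the primary difference may give up precision at no saving.

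**Working it through.** **1. Secondary non-inferiority, set side by side**

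| Antigens | Protocol 9.3.4: difference, CI, -10% rule | SAP 7.6 hypothesis | SAP 7.7 difference and CI | SAP 7.7 -10% rule |
|---|---|---|---|---|
| Polio 1, 2, 3 (C1-S1) | yes | yes | yes | yes |
| PT, FHA, PRN (C2-S2) | yes | no | yes | no |
| Diphtheria, tetanus (C2-S2) | yes | no | no | no |

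For diphtheria and tetanus the SAP plans seroprotection rates, Clopper-Pearson intervals for each group, and a CMH test. None of these is an interval for the difference. No arithmetic applies.

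**2. The plan's own sample size**

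Inputs (Protocol 9.1, SAP 4.3): 90% in the control group, equal rates assumed, margin 10 points, one-sided 0.025, power 93.3% per serotype. The Farrington-Manning null rates are 83.1% and 93.1%, so s0 = sqrt(0.831 x 0.169 + 0.931 x 0.069) = 0.452 and s1 = sqrt(2 x 0.9 x 0.1) = 0.424.

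n = [(1.960 x 0.452 + 1.501 x 0.424)/0.10]^2 = 231.8, i.e. 232, against the stated 233.

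Evaluable per group: 360 x 0.85 x 0.90 = 275. Power per serotype at 275: (0.10 x sqrt(275) - 1.960 x 0.452)/0.424 = 1.82, or 96.6%. The planned 93.3% is exceeded without any serostatus adjustment.

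**3. What serostatus strata would gain**

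The documents give neither the seropositive share nor rates by serostatus. Assume share f seropositive, of whom p show a 4-fold rise; 99% response in seronegatives; and a share m with no post-vaccination sample. Under LOCF the baseline value is carried forward, so neither rule can be met and the infant counts as not converted.

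P = (1-m)[fp + 0.99(1-f)]

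Variance cut = f(1-f)[(1-m)(0.99-p)]^2 / [P(1-P)]

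Example, f = 0.3, p = 0.7, m = 0: P = 0.903; 0.21 x 0.29^2 / (0.903 x 0.097) = 0.01766/0.08759 = 20.2%.

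| Assumed mix | Overall rate, complete data | PPS (m = 0) | FAS, m = 15% | FAS, m = 23.5% |
|---|---|---|---|---|
| 30% seropositive, 70% respond | 90.3% | 20.2% | 7.2% | 4.8% |
| 50% seropositive, 80% respond | 89.5% | 9.6% | 3.6% | 2.4% |
| 30% seropositive, 90% respond | 96.3% | 4.8% | 0.8% | 0.5% |

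Here 23.5% = 1 - 0.85 x 0.90. The first two mixes match the planned 90%. With equal rates in both serostatus groups the cut is zero.

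For the 30%/70% mix, simulated power per serotype (score interval, no true difference) goes from 97.2% to 98.4% in the PPS and from 88.6% to 90.5% in the FAS with 15% missing.

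**4. The unnamed interval**

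Simulated one-sided error per serotype at a true deficit of 10 points, site strata only, 275 per arm in assumed sites of 138/69/68:

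| S1 rate | Mantel-Haenszel (stratum-wise or Sato variance) | Stratified score |
|---|---|---|
| 90% | 2.7% | 2.4% |
| 98.6% | 3.5-3.6% | 2.2% |
| 99.5-99.6% | 3.9-4.0% | 2.1% |

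In the FAS at rates of 76-85%, all three intervals give 2.5-2.6%. The smallest passing C1 count, checked without stratification (Wald against score), is 236 under both if S1 is 248/275, 254 or 255 if S1 is 271/275, and 256 or 257 if S1 is 274/275.

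With six strata (site by serostatus) and a deficit only in seropositives, PPS error is 1.1-2.0% for the score interval and 2.4-2.8% for Sato. In the FAS with 15% missing it is 2.3-2.5% and 2.4-2.5%.

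**The case against.** **The protocol already fixes the rule.** This is correct. A reader might infer that no criterion for diphtheria, tetanus or pertussis was set in advance. The documents do not support that, because Protocol 9.3.4 gives the difference, the interval and -10%. The defect is that the SAP omits it while claiming consistency.

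**The site-only polio analysis is sound.** This also stands. It follows the randomisation factor, and power in evaluable infants is above plan. A reader might infer that the primary comparison is biased or underpowered for lack of serostatus strata; neither follows. The FAS power of 88.6% in the example reflects counting missing samples as failures. Serostatus strata recover only about 2 points of it.

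**The serostatus gain rests on assumed mixes.** True. It can be negligible, and in the FAS it is small at any mix that fits the plan.

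**The unnamed interval hardly matters.** Largely true. A reader might infer that the primary claim runs at nearly 4% error. That needs S1 rates near 99.5%. The figures of that size in Protocol 2.2.2.1 are adjusted for maternal antibody, and the plan assumes 90%. All three serotypes must also pass (Protocol 9.5), so the per-serotype error is only an upper bound. A score interval is not clearly better either, since with six strata it can be conservative in the PPS.

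**The ANCOVA site coding affects only supportive GMC ratios.** True, which is why it is only an improvement.

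**Conclusion.** The gap for diphtheria, tetanus and pertussis is an error in the SAP as written. It rests on the text alone and needs no assumption. It is minor because the protocol rule exists and the data will be available, but it is the item to correct first.

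The country coding in the C2/S2 ANCOVAs is an inconsistency that costs nothing to correct; its effect cannot be computed from the documents.

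Serostatus stratification is an optional gain in precision. For mixes that match the planned 90%, it is worth about 10-20% of the variance in the PPS and about 2-5% in the FAS at 23.5% missing (3.6-7.2% at 15% missing). It is worth about nothing if rates do not differ by serostatus. The interval should be named for completeness; in the cases checked, the choice moves the pass threshold by at most one infant in 275.

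**What to change.** 1. **SAP 7.6 and 7.7 (correction).** Add the secondary hypotheses. For diphtheria, tetanus, PT, FHA and PRN, state the site-stratified C2-S2 rate difference, its 95% CI by a named method, and the -10% criterion of Protocol 9.3.4. This makes the statement in SAP 2.3 true on this point.
2. **SAP 7.7, C2/S2 ANCOVAs.** Use the three randomisation sites, as in the CMH tests and the polio ANCOVA.
3. **SAP 7.7 and Protocol 9.3.4, polio (improvement).** For each serotype, estimate C1-S1 with Mantel-Haenszel weights over site by baseline serostatus (below 1:8, at least 1:8). If a stratum is empty in one arm, pool the two Pakistan sites within that serostatus. Keep the site-only result as a sensitivity analysis. State the interval: a Mantel-Haenszel interval with Sato variance is acceptable; a stratified score interval is also possible if its conservatism in sparse strata is accepted.

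The cost is wording and programming, with no new data or visits. Some of the six strata may be sparse. SAP 2.1 says the SAP is finalised before database lock. Item 3 changes the primary estimate, so it should be fixed before antibody results are linked to group. If that is no longer possible, keep the site-only estimate as primary and report the serostatus version as supportive.
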